Other contraindications for varenicline include suicidal ideation.²¹ Suicidality will be assessed at prior to randomization and during the follow-up assessments. If an individual endorses suicidality during the pre-randomization screening, they will be marked as ineligible for the study. This will be assessed using the PHQ9 toolkit for suicide ideation (refer to assessments section). An alert is programmed into the REDCap system that if an individual indicates an active plan to either physically harm or kill themselves, an alert will be sent to the study team. They will then be contacted by our clinical team to complete a risk assessment over via phone. A member of the clinical team will query the participant for details regarding the suicidal ideation, including a likelihood of harming oneself imminently and a plan for committing suicide. If the participant reports an imminent likelihood of harming him/herself or a plan for committing suicide, the clinical team member will call emergency services and will remain on the phone with the participant until emergency services arrive. In the event that the participant expresses an imminent likelihood of harming him/herself, and

the connection is lost, emergency services will be contacted to provide emergency services with the participant's contact information, including address. If the participant is not in imminent danger, the clinical staff will provide referrals for local mental health resources and/or instruction to go to the ED or call 911 should suicidal ideation worsen. The clinical team member will suggest that the participant seek treatment and then will follow-up with the participant via phone one week later.

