In the event that a participant endorses suicidal ideation but is not responsive to clinical staff's phone call within 48 hours, the participant will be emailed a list of local mental health resources and will suggest that the participant seek additional treatment. The email will also ask that the participant respond to the clinical staff either via phone or e-mail within 24 hours to confirm receipt of the treatment referrals. Should the participant not respond to the clinical staff's email within an additional 48 hours (4 days from completion of the assessment) and endorse "Several days", "More than half the days" or "nearly everyday" to "Thoughts that you would be better off dead or of hurting yourself in some way" on the PHQ9 suicidality toolkit at study screening, emergency services will be contacted and will be provided with the participant's name and address.

We will utilize the PHQ9 assessment to track depression and suicidal ideation during the baseline assessments. If suicidal ideation is endorsed, an automated "red flag" will be processed through our REDCap database. This red flag will indicate either a a) clinically significant increase in total PHQ scoring with an overall score of at least 15 (>5 point increase from baseline and resulting score >15), OR b) any value >0 for item 9/suicidal ideation). The red flag indicators will be monitored daily by our clinical team and will be met with the appropriate measures. These measures are based on prior MUSC-IRB approved protocols of varenicline (i.e., the STARS Pro00098479).

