Pharmacotherapy: Twenty participants will be randomized to receive active varenicline. Prior to randomization, the study physician, [name] or nurse practitioners from the Tobacco Treatment Service/PI [name] will conduct a pre-randomization medical review to ensure that they qualify for varenicline based on study eligibility criteria collected during primary (e.g., smoking history, age, medical history, and comorbidities) and secondary screening (psychiatric history, suicidal history, pregnancy status). A summary report that we create within our REDCap screening database, will be delivered electronically to study physician/nurse practitioners/PI [name]. They will review each participant's information and will determine whether to 1) accept the individual into the study, 2) reject the individual into the study (i.e., not eligible for varenicline), or 3) ascertain more information from the individual before either the decision to accept/reject the participant. The study physician/nurse practitioners may contact the individual to engage in further clinical interviewing of the potential participant. The disposition of each participant will be tracked within this screening database, allowing us to complete all CONSORT steps to study flow. The individual will not proceed to randomization and intake until we have signed, explicit documentation from the study physician/nurse practitioners/ PI [name] to do so. Thus, these procedures ensure that we retain physician/APRN oversight and approval of varenicline disbursement at the study outset. [name]/APRNs from the Tobacco Treatment Service retains their role in evaluation of adverse events as noted elsewhere within this application.

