6.2 Assessments

6.2.1 Efficacy

Study Assessments

The following tools will be used for the assessments conducted at baseline (week 0) and end of follow-up (Week 0, 8 & 12).

Demographics (Week 0): This questionnaire will collect basic demographic information for each subject including gender, ethnicity/race, employment status, etc.

Smoking/Tobacco Use History (Week 0): This will collect basic info about smoking and smoking cessation history, prior varenicline use, e-cigarette history, tobacco and nicotine product flavor preference, etc.

Modified Questionnaire on Smoking Urges (QSU) (Week 0, 8 & 12): This 3-item assessment is used to examine smoking related urges such as desire to smoke, anticipation of immediate positive outcome, etc.³¹E-cigarette Dependence (Week 0 & 8): The NIH Patient-Reported Outcomes Measurement Information System (PROMIS) measure for daily smokers has also been adapted to measure for use of other tobacco products.^{30, 40} This is a 4-item e-cigarette dependence questionnaire that measures withdrawal and craving.

E-cigarette Dependence Index (Week 0 & 8): This is a 10-item e-cigarette dependence questionnaire that measures difficulty quitting, withdrawal and cravings.⁵⁷

Subjective Effects Cigarettes and E-cigarettes (Week 0, Week 4): Participants will report on subjective evaluation about cigarettes and e-cigarettes. Subjective evaluation includes items derived from the Modified E-Cigarette Evaluation Questionnaire (meCEQ)⁵⁸ that have also been adapted for alternate tobacco products. It measures the degree to which participants experience reinforcing effects from smoking and e-cigarettes. The scale yields five clusters or domains: Smoking Satisfaction, Psychological Reward, Aversion, Enjoyment of Respiratory Tract Sensations, and Craving Reduction.⁵⁶

Patient Health Questionnaire-9 (PHQ9) (Week 0 and Bi-Weekly): which assesses for depression and includes an item on suicidal ideation.⁵⁰

Wisconsin Withdrawal Scale Brief (WSWS2-B): This 6-item scale assesses current symptoms of nicotine withdrawal including cravings and irritability.⁵⁹

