The data will be stored on secured server, laptop computer and desktop computer. The data will be stored in a locked room for 7 years after the final data is collected. After this point, the Data Manager and Principal Investigator, [name], will oversee the process in which data is destroyed or de-identified.

Several steps will be taken to safeguard the confidentiality of subjects and their data. All research data that is collected will be assigned a study participant number and that number will only identify participants in digital databases. The names of participants will not be associated with this data and assessments will be maintained according to participant study number. A master list connecting participant study numbers to participant names will be kept in a locked file cabinet where it can only be accessed by senior level project staff. Any information published as a result of the study will be such that it will not permit identification of any participant.

Right to privacy for participation in this research will be protected through alphanumeric coding of data (in place of names) and proper storage of research records, including treatment exit interviews. Collected materials will be maintained via an alphanumeric reference system maintained by [name]. Participants' names will appear only on the compound authorization form, and a master list maintained in a physically locked file that is separate from research data. Our data collection and management procedures are fully compliant with HIPAA. Access will be limited to personnel intimately involved in the study. A Certificate of Confidentiality will also be obtained. However, participants will also be told that if they present with suicidal or homicidal ideation and/or report any form of child/elder abuse or report plans to damage property then we will have to report this to the appropriate authorities and/or provide them with referrals for immediate treatment. Electronic data will be de-identified, and password protected. Only members of the study team will have access to the physical or electronic data.

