In the event that a participant endorses suicidal ideation but is not responsive to clinical staff's phone call within 48 hours, the participant will be emailed a list of local mental health resources and will suggest that the participant seek additional treatment. The email will also ask that the participant respond to the clinical staff either via phone or e-mail within 24 hours to confirm receipt of the treatment referrals. Should the participant not respond to the clinical staff's email within an additional 48 hours (4 days from completion of the assessment) and endorse "Several days", "More than half the days" or "nearly everyday" to "Thoughts that you would be better off dead or of hurting yourself in some way" on the PH-Q suicidality toolkit at study screening, emergency services will be contacted and will be provided with the participant's name and address.

We will utilize the PHQ9 assessment to track depression and suicidal ideation during the baseline assessments. If suicidal ideation is endorsed, an automated "red flag" will be processed through our REDCap database. This red flag will indicate either a a) clinically significant increase in total PHQ scoring with an overall score of at least 15 (>5 point increase from baseline and resulting score >15), OR b) any value >0 for item 9/suicidal ideation). The red flag indicators will be monitored daily by our clinical team and will be met with the appropriate measures. These measures are based on prior MUSC-IRB approved protocols of varenicline (i.e., the STARS Pro00098479).

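### The final four-day emergency-contact step for a silent participant depends on an item-9 answer at screening, so ideation first reported on study cannot trigger it

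*Combined protocol and SAP*

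**What the plan says.** Section 3.2.1 (Potential Risks) describes what happens when someone endorses ideation and does not answer the clinical team's call. After 48 hours, staff email a list of local resources, suggest treatment and ask for a reply. If a further 48 hours pass without one, and the person answered item 9 at the lowest positive level or above "on the PHQ9 suicidality toolkit at study screening, emergency services will be contacted", with name and address supplied. The Adverse Events text in Section 6.1.3 repeats this. Section 7.12 (Data Safety Monitoring Plan) has the same limit: "on the PH-Q suicidality toolkit at study screening, emergency services will be contacted".

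Three other statements bear on it:

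- Timing of assessment: "Suicidality will be assessed at prior to randomization and during the follow-up assessments". Section 6.2.1 lists "Patient Health Questionnaire-9 (PHQ9) (Week 0 and Bi-Weekly", and the table in Section 6.3.5 agrees.
- Consequence of a positive screen: "If an individual endorses suicidality during the pre-randomization screening, they will be marked as ineligible for the study".
- General response to a red flag, which includes any item-9 value above 0: "The red flag indicators will be monitored daily by our clinical team and will be met with the appropriate measures". The next sentence says these measures are based on an earlier varenicline protocol (STARS) approved by the MUSC IRB.

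**The concern.** The procedure is introduced as covering both screening and follow-up, and its clock starts when the assessment is completed. Its last step nevertheless looks back to the screening answer. A participant who screens negative, first reports thoughts of self-harm at a later PHQ-9, and then answers neither call nor email does not meet the written condition for contacting emergency services.

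The case may be rare, but it matters here. Section 6.3.1 describes exclusively remote procedures, so no clinic visit serves as a backstop, and Section 3.2.1 itself lists suicidal ideation as a contraindication for varenicline. For this participant the protocol gives explicit instructions up to the email and none after it.

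**Working it through.** This is a check of wording with very little arithmetic.

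**1. The stated time limit.** 48 h without an answer to the call + 48 h without a reply to the email = 96 h = 4 days. This reproduces the protocol's figure, assuming the call is placed when the assessment is completed.

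**2. The conditions for the final step.** As worded, three must hold together: (a) no response to call or email; (b) item 9 answered at the lowest positive level or above; (c) that answer given at screening. A participant on study can meet (a) and (b). The question is (c).

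**3. On-study answers.** An answer first given after screening fails (c) by definition, so the number of scheduled on-study PHQ-9s that can supply the qualifying answer is 0. The number of such assessments depends on what bi-weekly means:

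- every two weeks to Week 12 (Weeks 2, 4, 6, 8, 10, 12): 6 per participant, 6 × 40 = 240
- every two weeks to Week 8 only: 4 per participant, 4 × 40 = 160
- twice a week to Week 12: 24 per participant, 24 × 40 = 960

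These count assessments, not expected events.

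**4. Screening answers among enrolled participants.** Someone admitted with a positive screening answer could still meet (c). Whether such people exist depends on the item-9 value that makes a person ineligible. The protocol does not state it, suicidality is not among the numbered exclusions in Section 5.3.2, and under Section 5.1 the reviewing clinician may "ascertain more information from the individual before either the decision to accept/reject the participant". Taking item 9 as scored 0 to 3 (assumed; the protocol names three positive responses and flags any value above 0):

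| Ineligible at item 9 of | Screening values admitted | Of these, values meeting (c) |
|---|---|---|
| 1 or more | 0 | none |
| 2 or more | 0, 1 | 1 |
| 3 | 0, 1, 2 | 1, 2 |

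In the first row, which uses the protocol's own red-flag threshold, the step covers 0 of 40 correctly enrolled participants. In the other rows it covers only those admitted with a positive screening answer. In every row it misses ideation that first appears on study.

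**5. What else reaches a silent participant on study.**

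- The call and the email have no screening limit and apply.
- The active-plan alert applies, but needs a reported plan; item 9 asks about thoughts.
- The emergency-services steps during a call need the participant to report a plan or imminent risk, or to express imminent risk before the connection is lost. Someone who never answers triggers neither.
- The item-9 red flag applies and is reviewed daily, but the action is not spelled out beyond the reference to STARS.

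None of these states what to do once the email goes unanswered. No other section gives a wider version of the four-day step. The copy in Section 5.1 stops before any action; that may be text lost in extraction, and nothing here rests on it.

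**The case against.** The strongest reply is that the limiting phrase is a leftover. The procedure opens by covering follow-up, its clock runs from whichever assessment was completed, and it is repeated under Adverse Events and in the Data Safety Monitoring Plan, where a screening-only rule would be odd. That is a plausible account of the intent. It does not change what the three complete copies say, and it supports correcting them.

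The text also says when emergency services will be contacted without forbidding contact otherwise. Section 7.3 tells participants that if they present with suicidal ideation "then we will have to report this to the appropriate authorities and/or provide them with referrals for immediate treatment", and Section 7.9 likewise foresees intervention. This stands: staff have authority to act. What they lack is an explicit instruction.

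A reader might infer that ideation arising on study goes unaddressed, or that the four-day step is the only specific instruction for a silent participant. Neither is supported, because the alert, the daily flag review, the call and the email all operate on study. A reader might also infer that the two sites would act differently. The documents do not establish that: the measures are said to follow the STARS protocol, which is not among them and may or may not contain a wider rule.

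Finally, sending emergency services after an answer at the lowest positive level is a clinical and privacy judgement. But that threshold is already the protocol's own; the change extends it to later assessments without lowering it.

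**Conclusion.** The point holds as a gap in one step, and it should be fixed. Under any ineligibility cut-off, an item-9 answer first given on study cannot satisfy the written condition for contacting emergency services at four days. The further statement that the step covers no enrolled participant holds only if any item-9 value above 0 at screening excludes a person, which the protocol does not say. The rule is not empty even then, since it can still apply to people who endorse ideation at screening and are turned away.

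How many participants would be affected is unknown. The documents give no rate of new ideation and no rate of non-response to calls and emails, so the number could be zero. The REDCap alert logic is not in the documents either, so whether the programmed system shares the restriction cannot be judged.

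**What to change.** In Sections 3.2.1, 6.1.3 and 7.12, replace the phrase that limits the answer to study screening with: *at that assessment (screening or any later PHQ-9)*. Keep the existing item-9 threshold. The change works whatever value makes a person ineligible at screening.

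Then check that the REDCap alert follows the same rule, and that the consent wording covers giving a participant's name and address to emergency services on the strength of an on-study answer. Consent pages are not in the documents reviewed.

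The cost is an approved IRB amendment, as Section 7.2 requires for any protocol change, plus the two checks. In operation there may be a few more emergency contacts, some of them following an answer at the lowest positive level. Assessments, schedule, endpoints and sample size do not change.

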3.2.1 Potential Risks

The main study procedures include completion of questionnaires (minimal risk), varenicline use (use will be tracked as well as any new or recurring symptoms), and Truth Initiative texting services. This is a low-risk medication study (see text below). There is also a risk that the treatment the study participant is randomized to may prove to be less effective than the other study treatment or other available treatments (i.e., participants who receive placebo). We will conduct scheduled assessment throughout the intervention to review participant symptoms, mood, and wellbeing.

Breach of confidentiality: Study investigators across both sites have experience as an investigator dealing with such sensitive information and has experience assuring that data is adequately protected. Safeguards to protect confidentiality include locked records and firewalls around password-protected electronic data, and all study data being coded, with the key linking the code with a subject's identity being kept in a separate, locked file.

Assessments and Rating Scales: All assessments and rating scales are non-invasive and involve minimal risk to study participants.

Varenicline is an FDA approved smoking cessation medication. Black-box warnings were removed by the FDA in recent years following the large clinical EAGLES trial showing that this is a low risk medication.¹ Additionally, meta-analyses have been conducted that show varenicline as a safe and useful medication.¹⁷⁻²⁰ Some side effects of varenicline include nausea, constipation, indigestion, abdominal pain, heartburn, increased or decreased appetite, trouble falling asleep or staying asleep, unusual dreams or nightmares, headache, lack of energy, back, joint, or muscle pain, and abnormal menstrual cycles.

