A novel alert system will be built into the Adverse Event surveys REDCap database such that any severe adverse events (e.g., severe nausea, severe sleep disturbances, severe changes in mood) that are endorsed along with self-report of cessation of pharmacotherapy use will be monitored by research staff, who will consult with the study physician/APRN from the Tobacco Treatment Service/PI [name] when indicated for clinical assessment and management. We believe this alert system will improve varenicline medication adherence if the pharmacist/APRN/physician can quickly follow-up on any side effects that may be associated with pharmacotherapy use and call the patient with any recommended dose adjustments. All dose adjustments will be recorded in our REDCap database.

Guided Self-Change Pamphlet: All groups will receive this pamphlet as a brief behavioral component of the intervention. This 3-page pamphlet includes information on how to reduce and quit e-cigarettes on their own (on Page 1), how to prevent relapse to combustible cigarettes (for mono vapers who quit combustible cigarettes by vaping; on Page 2), and how to enroll in the online This is Quitting services (described above; on Page 3).

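### Read literally, the PHQ-9 red-flag rule fires only when suicidal ideation is endorsed, which would disable its total-score limb; that limb's cut-off is also stated two ways

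*Combined protocol and SAP*

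**What the plan says.** The rule appears in almost the same words in sections 3.2.1 (Potential Risks), 5.1 (General Design Description), 6.1.3 (Dosage, Administration, Schedule) and 7.12 (Data Safety Monitoring Plan). Its parts are:

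- **Trigger.** The sentence that introduces the flag begins "If suicidal ideation is endorsed, an automated".
- **Limb (a).** A rise in the PHQ-9 total with an "overall score of at least 15 (>5 point increase from baseline and resulting score >15".
- **Limb (b).** The definition continues "OR b) any value >0 for item 9/suicidal ideation".
- **Handling.** The clinical team checks flags daily and takes unspecified suitable measures.

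Three other statements bear on it. On eligibility, 3.2.1 says "If an individual endorses suicidality during the pre-randomization screening, they will be marked as ineligible for the study". On timing, it says "Suicidality will be assessed at prior to randomization and during the follow-up assessments"; section 6.2.1 and the table in 6.3.5 schedule the PHQ-9 at week 0 and bi-weekly. A separate REDCap alert works on a higher threshold: "if an individual indicates an active plan to either physically harm or kill themselves, an alert will be sent to the study team".

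**The concern.** An automated alert has to be built from explicit logic, and two programmers could build different alerts from this text. One would treat endorsed ideation as the condition for any flag. The other would treat limbs (a) and (b) as independent triggers. They part company in the case that limb (a) appears to be written for: marked worsening of depression without endorsed ideation.

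That case matters here because anyone who endorses suicidality before randomization is excluded. Randomized participants should therefore start with item 9 at 0, and limb (a) is the only PHQ-9 total-score alert for worsening that stops short of ideation. The trial is run remotely, so an automated flag is a main route by which a PHQ-9 score prompts clinical review.

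The conflict over the cut-off is a strict contradiction within one sentence, but a narrow one.

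**Working it through.** The plan gives no figure to reproduce. The check takes the logic of the rule and then counts the scores at which the readings differ.

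**Inputs.** From the documents: a rise of more than 5 points; a cut-off of 15 or more, or above 15; item 9 above 0; 40 participants; 12 weeks, of which 8 are on treatment; PHQ-9 bi-weekly after week 0. Assumptions, not stated in the documents: nine items each scored 0 to 3, and bi-weekly meaning every two weeks. With item 9 at 0, the other eight items give totals of 0 to 24, which is 25 values.

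**Step 1: the trigger.** Let A mean that limb (a) is met and I that item 9 is above 0.

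- Ideation as a precondition: flag = I and (A or I) = I. Limb (a) drops out.
- Limbs as alternatives: flag = A or I. Limb (a) adds every case with A true and item 9 at 0.

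Example: 5 to 20 with item 9 at 0. The rise is 20 − 5 = 15, which exceeds 5, and 20 passes either cut-off. The first build raises no flag; the second does.

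**Step 2: how many score pairs depend on the trigger.** Take item 9 at 0 at both visits, so there are 25 × 25 = 625 baseline/follow-up pairs. For a follow-up total f, a rise of more than 5 allows baselines 0 to f − 6, which is f − 5 values.

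- Cut-off 15 or more: f = 15 to 24 gives 10 + 11 + … + 19 = 145 pairs (145/625 = 23%).
- Cut-off above 15: f = 16 to 24 gives 11 + 12 + … + 19 = 135 pairs (135/625 = 22%).

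**Step 3: the cut-off.** The difference is 145 − 135 = 10 pairs, all with a follow-up total of exactly 15 and a baseline of 0 to 9. Example: 9 to 15 is a rise of 6; it is flagged at 15 or more and not at above 15. If item 9 is above 0, limb (b) fires and the cut-off makes no difference.

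**Step 4: how often the rule is applied.** Follow-up PHQ-9s fall at weeks 2, 4, 6, 8, 10 and 12: 6 × 40 = 240, of which 4 × 40 = 160 are on treatment and 2 × 40 = 80 after it. This assumes full retention and response, so it is an upper limit.

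The counts in steps 2 and 3 are unweighted score combinations. They are not expected numbers of flags or patients.

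**The case against.** The strongest reply is that the sentences can be reconciled. The lead-in does not say that ideation is the only trigger; the next sentence defines the flag with an explicit OR; and the sentence before names depression as well as ideation as what is tracked. A programmer would have to override the OR to build the restrictive version. The measures are also said to follow a prior IRB-approved varenicline protocol. Much of this stands: the likely intent is that limb (a) works alone. But likely intent is not a specification, and no section settles the point.

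The second reply is that other safeguards exist, and this also stands. Section 3.2.1 says "We will conduct scheduled assessment throughout the intervention to review participant symptoms, mood, and wellbeing". Section 6.2.1 has weekly mood items, 6.2.3 weekly adverse-event ratings, and 7.11 a weekly team review. Section 5.1 adds an alert for severe adverse events, including "severe changes in mood) that are endorsed along with self-report of cessation of pharmacotherapy use will be monitored by research staff". Whether that alert also requires the participant to have stopped the medication is unclear, though the following sentence, on dose adjustment, favours the broader reading. None of these is a PHQ-9 total-score alert.

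A reader might also infer more than the documents support:

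- *That worsening depression or suicidality would be missed.* Limb (b) works under every reading, and the checks above remain.
- *That the PHQ-9 is given only at baseline*, because the red-flag paragraph mentions baseline assessments. Sections 6.2.1 and 6.3.5 schedule it through follow-up.
- *That REDCap is wrongly programmed.* The documents do not show its logic.
- *That the trigger decides the outcome over most of the score range.* Limb (a) can be reached from 19 of 25 baselines (0 to 18), but it is met in only 145 of 625 pairs.
- *That the rule applies 960 times*, taking bi-weekly as twice a week (24 × 40). The PHQ-9 sits under the weekly column as a bi-weekly exception, and the routine surveys are weekly, so this is implausible.

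**Conclusion.** The rule is internally inconsistent as written and should be corrected. The main defect is the trigger: taken literally, it makes limb (a) redundant, which affects 145 (15 or more) or 135 (above 15) of 625 possible score pairs with item 9 at 0. The cut-off conflict is minor, at 10 pairs. Both counts assume nine items scored 0 to 3.

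The consequence is limited to the automated score-based flag, at no more than 240 scheduled follow-up PHQ-9s. No endpoint or efficacy analysis is touched. This is a correction of wording and alert logic for a stated safety rule, not evidence that an alert has failed.

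**What to change.** In sections 3.2.1, 5.1, 6.1.3 and 7.12, replace the lead-in and definition with one rule:

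> At each bi-weekly PHQ-9 a red flag is raised if (a) the total has risen by more than 5 points from baseline and is 15 or more, or (b) item 9 is above 0, either alone being sufficient. Limb (b) also applies at baseline.

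The clinical team should confirm the cut-off of 15 or more, which is the more cautious of the two. State also that bi-weekly means every two weeks.

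Add that a limb (a) flag without ideation prompts contact from the clinical team. The detailed response steps in 3.2.1 are all keyed to ideation, so correcting the trigger alone would leave such a flag without a defined response.

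Then check the REDCap logic with two test cases, both with item 9 at 0: 9 to 15 and 5 to 20. Both should raise a flag under the rule above.

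The cost is the same edit in four places, one added sentence on response, and one logic check. The downside is a few more flags for daily review: totals of exactly 15 from baselines of 0 to 9 and, if REDCap now follows the lead-in, all limb (a) flags with item 9 at 0.
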